### 10.4.2 Analysis of the Primary Efficacy endpoint(s)

The efficacy analysis will be performed based on the FAS as primary analysis and on the PPS as supportive analysis.

### **Progression Free Survival (PFS)**

Progression free survival is defined as the time, in months, from treatment initiation (Cycle 1 , day 1) to the date of the first documented disease progression or death due to any cause, whichever comes first. Clinical deterioration will not be considered progression. For subjects who neither progress nor die, the survival time will be censored at the date of their last disease assessment. For subjects who start a new anti-tumor treatment, survival time will be censored at the date of the start of the new treatment.

The PFS function will be estimated using the Kaplan-Meier product-limit method. Median and two-sided confidence intervals (CI) for median PFS will be computed by and Kaplan-Meier plots of PFS will be presented.

Absolute frequencies and proportions of patients with disease progression or all-cause death will also be provided.

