## 7. Study procedures and Schedule

### 7.1 Study Procedures/Evaluations

#### 7.1.1 Efficacy Assessments

The primary endpoint of this study is Progression Free Survival (PFS). Secondary efficacy endpoints are Overall Survival (OS), Overall Response Rate (ORR), Renal Response Rate (RRR), duration of response and time to next therapy.

Response or disease progression will be assessed by the Investigator based on the analysis of serum and urine protein electrophoresis (sPEP and uPEP), serum and urine immunofixation (sIFE, uIFE), serum free light chain protein (sFLC), imaging and bone marrow assessments as per IMWG guidelines (see [Appendix 4](#)). If the patient does not have documented disease progression as defined in [Appendix 4](#) at the time of study drug discontinuation, then tumor assessments must continue to be performed according to the same schedule shown in [Table 7.2](#) until disease progression even if a subsequent anti-myeloma treatment is started prior to disease progression.

Assessment of renal response will be conducted in accordance with the International Myeloma Working Group (IMWG) response criteria, based on eGFR calculated by the CKD-EPI formula.

All study assessments and laboratory tests will be performed according to standard clinical practice and as clinically indicated.

Assessments performed at external laboratories may be accepted as per institutional practice.

Disease assessments are shown in Table 7.1.

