### **Sponsor confirmation of progressive disease**

A diagnosis of progressive disease (that is also confirmed with a consecutive assessment if based on M-protein/serum FLC levels) must be reported, via email, to the sponsor's Medical Reviewer within 1 working day using the Progressive Disease Notification Form together with all supporting documentation for the diagnosis. The Medical Reviewer will check that the investigator's assessment of PD is in line with the IMWG criteria and will provide a confirmation on the same form and return it via email to the site. In the case that the investigator's assessment is not deemed in line with the IWG criteria, the Medical Reviewer will provide comments in the relevant section of the notification form and may also contact the investigator to discuss the subject further.

Study treatment discontinuation and start of subsequent anti-myeloma therapy should occur only after sponsor confirmation of PD.

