## 7.2.3 Follow-up Period

### Post-treatment follow-up

Patients who discontinue treatment for reasons other than documented disease progression, death, lost to follow-up, or withdrawal of consent should continue to be followed for response assessments every 4 weeks as in [Table 7.2](#). The reason for completion/discontinuation should be recorded on the eCRF.

If a patient starts new anti-neoplastic therapy prior to disease progression, every attempt should be made to perform tumor evaluations until documented disease progression. In addition, all new anti-neoplastic therapy administered starting from the last dose of the study treatment until death, lost to follow-up, or withdrawal of consent will be recorded in the eCRF.

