## 10.4 Description of Statistical Methods

### 10.4.1 General Approach

All data collected in this study will be listed and summarized as appropriate as described below. Data from all sites will be pooled and summarized.

Continuous data will be summarized by mean, standard deviation, median, first and third quartiles, minimum and maximum. Categorical data will be presented by absolute and relative frequencies (n and %) or contingency tables.

One-sided alpha level 0.025 will be considered. No alpha level adjustment will be carried out for primary and secondary outcome variables.

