## 10.5 Sample Size

The calculations were based on previous data for daratumumab in patients with relapse or refractory myeloma. The median PFS with daratumumab treatment in the SIRIUS study was 5.6 months in patients who received daratumumab at the dose of 16 mg/kg.

In order to test at  $\alpha=0.05$  the null hypothesis that the PFS is less than 3 months versus the alternative hypothesis that PFS is at least 5 months with a power of 90%, 34 patients must be included in the study. This calculation assumes exponential survival curves, an accrual time of 18 months and a length of follow up period of 30 months. Assuming a drop-out rate of about 10%, 38 patients are needed.

Sample size was computed by “SWOG One arm survival sample size and power” ([www.swogstat.org/stat/public/one\\_survival.htm](http://www.swogstat.org/stat/public/one_survival.htm))

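### Primary PFS is censored at any new anti-tumor treatment, with no 'before documented progression' qualifier, and no analysis uses the progressions collected after a switch

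*Protocol*

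**What the plan says.** Protocol 10.4.2 times PFS from Cycle 1 Day 1 "to the date of the first documented disease progression or death due to any cause, whichever comes first". It adds: "Clinical deterioration will not be considered progression". Patients with neither event are censored at their last disease assessment. A separate sentence covers switching: "For subjects who start a new anti-tumor treatment, survival time will be censored at the date of the start of the new treatment". SAP 6.6.1.3 repeats that sentence word for word. Neither document says that it applies only when no progression has yet been documented. Neither says which date governs for a patient who switches without progression or death, and who therefore meets both censoring rules.

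Progression data are nevertheless collected after a switch. Protocol 7.1.1 requires assessments on the same schedule "until disease progression even if a subsequent anti-myeloma treatment is started prior to disease progression". Protocol 7.2.3 says: "If a patient starts new anti-neoplastic therapy prior to disease progression, every attempt should be made to perform tumor evaluations until documented disease progression".

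Protocol 7.1.1, under sponsor confirmation of progressive disease, limits early switching: "Study treatment discontinuation and start of subsequent anti-myeloma therapy should occur only after sponsor confirmation of PD".

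Duration of response takes over the PFS censoring (Protocol 10.4.3, SAP 6.6.1.4). The per-protocol analysis changes the population, not the censoring. Time to next therapy counts a switch as an event, but it is a separate secondary endpoint. Neither document plans a PFS analysis that uses progression after a switch.

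**The concern.** Kaplan-Meier estimation treats a censored patient as having the same future risk as those still followed. That fails if a patient is moved to another therapy because the disease is getting worse: the patient leaves the risk set shortly before an event that would have counted. The exclusion of clinical deterioration makes this more likely. Appendix 4 lists a creatinine rise of 2 mg/dL or more and a hemoglobin fall of 2 g/dL or more under clinical relapse, which does not count towards PFS. In patients with eGFR below 30 or on dialysis, either could plausibly prompt a change of therapy before progression is confirmed.

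The trial has one arm and reads PFS against "the null hypothesis that the PFS is less than 3 months". With no control arm subject to the same censoring, an upward shift in the median passes straight into the conclusion.

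**Working it through.** **Inputs.** From Protocol 10.5 (repeated in SAP 6.4.2): null median 3 months, alternative 5, power 90%, alpha 0.05, exponential survival, 18 months of accrual, 30 months of follow-up, 34 patients, 38 after about 10% drop-out. From Protocol 4.1: 24 months of accrual and 13 months of follow-up for the last patient. The share q of patients who switch before progression and the lead time L are not in the documents; both are assumed.

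**The plan's own figure.** Events needed: d = (z_alpha + z_beta)² / [ln(5/3)]². At one-sided 0.05, d = (1.645 + 1.282)² / 0.261 = 32.82. The event probability under a 5-month median is 0.994, so N = 32.82 / 0.994 = 33.01, rounded up to 34, and 34 / 0.9 = 37.8, rounded up to 38. The plan's figures reproduce at one-sided 0.05. At one-sided 0.025, d = 40.27 and N = 40.5, rounded up to 41. So the illustration below uses the sizing alpha of 0.05 and also shows 0.025.

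**Simulation.** Each trial has 38 patients. Time to event T is exponential with median 3 months. Entry is uniform over 24 months and data are cut at month 37. A share q of patients is censored at T − L, with L = 0.5 or 1 month. The test statistic is Z = √D × ln(m/3), where D is the number of events and m = ln 2 × (total follow-up) / D. Rejection is Z > 1.645 at 0.05 or Z > 1.960 at 0.025. There were 4,000 trials per setting, and the KM median comes from a sample of 400,000.

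| q | L (months) | KM median | Events of 38 | Rejects at 0.05 | Rejects at 0.025 |
|---|---|---|---|---|---|
| 0 | - | 3.0 | 37.7 | 0.038-0.039 | 0.017-0.018 |
| 5% | 1.0 | 3.08 | 36.1 | 0.059 | 0.029 |
| 5% | 0.5 | 3.11 | 36.0 | 0.071 | 0.037 |
| 10% | 1.0 | 3.17 | 34.7 | 0.095 | 0.048 |
| 10% | 0.5 | 3.25 | 34.3 | 0.111 | 0.058 |
| 20% | 1.0 | 3.37 | 31.7 | 0.172 | 0.102 |
| 20% | 0.5 | 3.55 | 30.9 | 0.240 | 0.147 |

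The table lets only patients with T > L switch. If those who would progress sooner may also switch, close to day 0, rejection at 20% and L = 0.5 rises to 0.27-0.29. Across such coding choices and repeat runs the ranges at 0.05 are about 6-7%, 8-12% and 17-29%. In trials of 38 the typical KM median is about 3.1 months without switching and about 3.4-3.7 at 20%.

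**Switching unrelated to progression.** With switch times drawn independently of T, rejection at 0.05 stays at about 0.04 for 5, 10 and 20% switchers, and the KM median stays at 3.0-3.1 months.

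**Moving the censoring date.** With 4-weekly assessments and censoring at the last assessment before the switch, rejection at 0.05 is 0.100 instead of 0.114 at 10% switchers and 0.235 instead of 0.271 at 20%. Redating alone leaves most of the bias in place.

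**The case against.** A reader might infer that the rule censors patients who progress first and then switch. Taken literally it would. If half the patients started new therapy one month after progression and were censored there, a true median of 3.0 months would read as 6.7, and only 19 of 38 would count as events, below the 20-event trigger. The documents do not support this as the intent. The PFS clock stops at the first documented progression or death, duration of response applies PFS censoring only to responders without a progression event, and progression is the normal precondition for new therapy. It is a gap in wording.

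A reader might also infer that the rule can only raise PFS. That holds only for switches linked to worsening disease.

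The strongest objection is that requiring sponsor confirmation before new therapy is aimed at this very mechanism, and that concomitant anti-myeloma therapy is prohibited on treatment (Protocol 7.3.2). This stands to a large extent: early switches should be few, and the 20% row has no anchor in the documents. It does not remove the point. Protocol 5.3.1 and 6.1.5 require treatment to stop for reasons other than progression (adverse events, infusion reactions, toxicity holds beyond 28 days), which sits uneasily with a rule that treatment stops only after confirmed progression; those passages need to be reconciled. Sections 7.1.1 and 7.2.3 expressly foresee a switch before progression. Stops for toxicity need not be linked to prognosis, however, and to that extent they do no harm.

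The rejection rates also belong to a test that the analysis sections do not name. Those sections plan a KM median with a two-sided confidence interval and state: "One-sided alpha level 0.025 will be considered". In practice the bias would act through the median and its interval.

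Time to next therapy would make early switching visible, which is a partial safeguard, but it does not correct PFS.

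**Conclusion.** The point holds in a limited form. The missing qualifier and the two competing censoring dates are wording gaps to close. What remains is informative censoring of patients who switch before progression because their disease is worsening, with no planned analysis that would show its effect although the data are collected. Its size depends on a switch rate that the documents do not give. At 5% the effect is small: the large-sample median moves from 3.0 to about 3.1 months, and the illustrative error from 4% to 6-7%. At 10% the error is 8-12%. At 20% it is 17-29%. These figures assume exponential times, a true median of 3 months, a switch 0.5 to 1 month before progression in every switcher, and an exponential test at one-sided 0.05. They illustrate what could happen; they do not show that the primary result will be inflated. The change is still worth making, because a single-arm comparison with a fixed null has nothing to offset such a bias.

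**What to change.** 1. In Protocol 10.4.2 and SAP 6.6.1.3, limit the rule to subjects who start a new anti-tumor treatment before documented progression or death, and state one censoring date. This clarifies the rule but does not remove the bias.
2. In SAP 6.6.1.3, pre-specify a sensitivity analysis on the full analysis set that counts the first progression or death whenever it occurs, regardless of new therapy. Preferably add a second that counts a switch before progression as an event, because effective next-line therapy can delay progression in the first.
3. Report the number of patients censored for new therapy. Show all medians and confidence intervals side by side against 3 months, and state whether the conclusion about the 3-month null is the same in each.

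The cost is a wording change and one or two extra Kaplan-Meier runs on data already required, with no new visits or patients. The sensitivity median may come out slightly lower. If early switches are rare the analyses will nearly coincide, which would strengthen the primary result.

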## 10.2 Statistical Hypotheses

The primary efficacy endpoint is PFS as assessed by the Investigator.

The expected median PFS with daratumumab treatment in the SIRIUS study was 5.6 months in the patients who received daratumumab at the dose of 16 mg/kg.

In order to test at  $\alpha=0.05$  the null hypothesis that the PFS is less than 3 months versus the alternative hypothesis that PFS is at least 5 months with a power of 90%, 34 patients must be included in the study. This calculation assumes exponential survival curves, an accrual time of 18 months and a length of follow up period of 30 months. Assuming a drop-out rate of about 10%, 38 patients are needed.

The distribution of PFS will be estimated using the Kaplan-Meier method. The median PFS along with 95% confidence intervals will be presented (see Section 10.4.2).

The analysis will be performed when at least 20 PFS events have been documented.

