6.4.2 Sample Size and Power Calculations

The calculations were based on previous data for daratumumab in patients with relapse or refractory myeloma. The median Progression Free Survival (PFS) with daratumumab treatment in the SIRIUS study was 5.6 months in patients who received daratumumab at the dose of 16 mg/kg.

Health Data Specialists	
DARE (EAE-2017/MM02)- Statistical Analysis Plan	Version: 1.0 EN
Author: GC, Reviewer: MS, Quality Assurance: GK	Date: 02-02-2018

In order to test at $\alpha=0.05$ the null hypothesis that the PFS is less than 3 months versus the alternative hypothesis that PFS is at least 5 months with a power of 90%, 34 patients must be included in the study. This calculation assumes exponential survival curves, an accrual time of 18 months and a length of follow up period of 30 months. Assuming a drop-out rate of about 10%, 38 patients are needed.

Sample size was computed by “SWOG One arm survival sample size and power” (www.swogstat.org/stat/public/one_survival.htm)

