6.6 Statistical Methodology

All statistical analyses will be performed using SAS® version 9.4 (64-bit) or later, a validated statistical software package, (SAS Institute, Inc., Cary, NC, USA).

Data from all sites will be pooled and summarized. Continuous data will be summarized by mean, standard deviation (SD), median, first and third quartiles, minimum and maximum. Categorical data will be presented by absolute and relative frequencies (n and %) or contingency tables.

One-sided alpha level 0.025 will be considered. No alpha level adjustment will be carried out for primary and secondary outcome variables.

The primary efficacy endpoint is PFS for patients, who received daratumumab at the dose of 16 mg/kg, as assessed by the Investigator. The distribution of PFS will be estimated using the Kaplan-Meier method. The median PFS along with 95% confidence intervals will be presented (see Section 6.6.1.3). The analysis will be performed when at least 20 PFS events have been documented.

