6.6.1.2 Statistical tests

Association between categorical variables will be assessed using either chi-square test (χ^2), Fisher exact test or McNemar test, as appropriate (Table 4). Furthermore, in order to examine the differences in the values of continuous variables at different time periods, Wilcoxon signed rank test for related samples and U-Mann Whitney test for independent samples will be used (Table 5).

Medical history and safety will be coded by MedDRA (the most updated version available) while System Organ Class (SOC) and Preferred Term (PT) will be tabulated in frequency tables (N, %).

Concomitant medication(s) will be coded through the ATC Drug Classification dictionary by WHO Collaborating Centre for Drug Statistics Methodology in terms of therapeutic subgroup, chemical subgroup and chemical substance and will be presented in frequency tables.

Health Data Specialists	
DARE (EAE-2017/MM02)- Statistical Analysis Plan	Version: 1.0 EN
Author: GC, Reviewer: MS, Quality Assurance: GK	Date: 02-02-2018

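### A PFS hypothesis (3 versus 5 months, 90% power) is stated and sized, but no test or success rule decides it

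*Protocol*

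**What the plan says.** **Hypothesis and sizing.** Protocol 10.2 sets "the null hypothesis that the PFS is less than 3 months versus the alternative hypothesis that PFS is at least 5 months". Protocol 10.5 and SAP 6.4.2 repeat it at alpha 0.05, with sidedness not given. SAP 6.4.2 concludes that "with a power of 90%, 34 patients must be included in the study", raised to 38 for about 10% drop-out. On the model, Protocol 10.5 states: "This calculation assumes exponential survival curves, an accrual time of 18 months and a length of follow up period of 30 months". A one-arm survival calculator is cited, for the sample size only.

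**Primary analysis.** Protocol 10.4.2 and SAP 6.6.1.3 provide a Kaplan-Meier curve, event counts and proportions, and this: "Median and two-sided confidence intervals (CI) for median PFS will be computed by and Kaplan-Meier plots of PFS will be presented". Protocol 10.2 supplies the level: "The median PFS along with 95% confidence intervals will be presented". SAP 6.6 does the same.

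**Alpha and timing.** Protocol 10.4.1: "One-sided alpha level 0.025 will be considered". Protocol 10.4.9 and SAP 6.6 agree, but none of the three attaches this alpha to a PFS test. SAP 6.6: "The analysis will be performed when at least 20 PFS events have been documented".

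**Tests named.** SAP 6.6.1.2 begins "Association between categorical variables will be assessed using either chi-square test" and goes on to Fisher, McNemar, Wilcoxon and Mann-Whitney. The only log-rank test in either document is for time to next therapy (Protocol 10.4.3, SAP 6.6.1.4).

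**The concern.** A power figure belongs to a specific test at a specific alpha and event count. Here the hypothesis, alpha and power are stated, but the analysis sections never compare PFS with 3 months. The reader cannot tell which result would reject the null, or whether the 90% applies to whatever is eventually done.

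The trial is open-label and single-arm, with PFS assessed by the investigator. An open decision rule could be settled after results are visible, and the same data could be called positive under one plausible rule and negative under another.

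**Working it through.** **1. Reproduce the plan's 34.** Inputs: 3 and 5 months read as medians, exponential PFS, 90% power, accrual 18 months, follow-up 30 months (Protocol 10.5). The documents write PFS rather than median PFS. Reading it as the median follows from the 5.6-month median they cite, and it reproduces 34.

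Events: d = (z_alpha + z_power)² / [ln(5/3)]², with ln(5/3) = 0.511.

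- One-sided 0.05: (1.645 + 1.282)² / 0.511² = 32.8 events. The event probability with a 5-month median is 0.994, so N = 32.8 / 0.994 = 33.01, rounded up to 34. A cube-root version gives 33.8, also 34. Then 34 / 0.90 = 37.8, giving 38. **Reproduced.**
- One-sided 0.025: (1.960 + 1.282)² / 0.511² = 40.3 events, N = 41 to 42. **Not reproduced.**

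The sizing therefore used one-sided 0.05.

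**2. Exact power of the exponential test.** Power = P(χ² on 2d df > (3/5) × upper-alpha critical value of χ² on 2d df).

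| Events | one-sided 0.05 | one-sided 0.025 |
|---|---|---|
| 33 | 90.3% | 85.0% |
| 20 | 75.8% | 66.8% |

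**3. What a rule based on the planned interval would do.** The rule is my assumption: success if the lower 95% Kaplan-Meier limit for the median exceeds 3 months (Brookmeyer-Crowley interval, three transformations). Simulation: 40,000 trials, N = 38, uniform entry over 24 months, exponential PFS in continuous time, exponential loss of about 10% (mean 3.7 patients), cut at month 37 (mean 33.0 events) or at the 20th event. The log-rank statistic is (E − D)/√E, with D the observed events and E those expected under a 3-month exponential.

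| At one-sided 0.025 | Power, month 37 (true median 5) | Power, 20th event (true median 5) | Type I error, month 37 (true median 3) |
|---|---|---|---|
| Interval rule, log-log | 44% | 32% | 1.7% |
| Interval rule, linear | 54% | 45% | 3.1% |
| Interval rule, log | 61% | 53% | 4.4% |
| One-sample log-rank | 83% | 60% | 1.7% |
| Exponential test | 86% | 67% | 2.6% |

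At one-sided 0.05 (90% interval), month 37, power is 59%, 66% and 71% for the interval rule, 89% for log-rank and 91% for the exponential test.

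**4. Sensitivity to loss** (month 37, one-sided 0.025). With no loss the interval rule has 45%, 58% and 58% and log-rank 86%. With 10% lost uniformly over months 0 to 5, the interval rule has 43%, 53% and 61% and log-rank 83%. The ordering does not change.

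**The case against.** - **A rule is implied.** Protocol 10.2 puts the hypothesis beside a 95% interval, and a two-sided 95% interval matches one-sided 0.025, so lower limit above 3 months is the natural reading. That is fair, but it is written nowhere and it is the low-power choice. If it was intended, the 90% is wrong for it.
- **Estimation suffices.** The objective is to evaluate PFS in a phase 2 trial, which a median and interval serve. This would hold if the plan did not also state a null, an alternative, an alpha and a power.
- **Much of the shortfall has other causes.** The fall from 90.3% to 85.0% comes from the two alphas and the figures at 20 events from the trigger. This stands. The part due to the missing test is the gap between the interval rule and a one-sample test at the same alpha and timing.
- **Twenty is a minimum.** Correct. About 33 events are expected by month 37, so the 20-event column is the earliest permitted case.
- **The 90% does not single out one test.** A one-sample log-rank test at one-sided 0.05 in the sizing design has 89%. The figure identifies the alpha more firmly than the test.
- **Progression is found at 28-day visits.** If every event is recorded at the next visit and the underlying median is 3 months, type I error at nominal 2.5% rises to 7.7% (exponential) and 5.7% (log-rank). With an underlying median of 5, interval-rule power rises to 56%, 65% and 72%. This overstates the effect for deaths, but the null must refer to PFS as documented, and the simulated figures are approximate.
- **The sentence on the interval breaks off.** A method name may have been lost from it, but neither document names one elsewhere.

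**Conclusion.** The concern holds. The plan states and powers a hypothesis that its analysis sections do not test, and it gives no success rule. At month 37 and one-sided 0.025, using the planned interval as the rule would cost 22 to 39 percentage points of power against a one-sample log-rank test (83 − 61 and 83 − 44). Its type I error would run from 1.7% to 4.4% against a nominal 2.5%, depending on an interval type that is not stated.

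These sizes assume exponential PFS, continuous event times, about 10% loss, 38 patients and a decision rule that I supplied for illustration. The absence of a test and of a success rule rests on the text alone. It should be fixed: the data remain usable, but the decision on the hypothesis is undefined.

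**What to change.** In Protocol 10.4.2 and SAP 6.6.1.3:

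- Name one primary test of the 3-month null: either the exponential test behind the sizing, or a one-sample log-rank test against an exponential null with median 3 months.
- State that this test, at one agreed one-sided alpha, decides the hypothesis, and that the null refers to documented PFS as defined in 10.4.2.
- Name the interval method and keep the Kaplan-Meier median and interval as the estimate.
- Restate power for the named test at the chosen alpha and event count. Naming the test alone does not restore 90% at one-sided 0.025 or at 20 events.

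**Cost.** A paragraph in each document, a few lines of code and no new data. Alpha and the event count must be settled together with the test, and dated before data review because the trial is open-label.

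**Downsides.** The test leans on the exponential null already assumed in the sizing. The restated power will be less favourable if alpha is one-sided 0.025 or analysis comes at 20 events. In continuous time the log-rank test is somewhat conservative (1.7% at nominal 2.5%, 3.9% at nominal 5%), while the exponential test is close to nominal (2.6% and 5.1%).
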